3.2. Dose Limiting Toxicity (DLT) Definition

Monitoring for DLTs will occur during Part 1. Severity of adverse events (AEs) will be graded according to National Cancer Institute Common Terminology Criteria for Adverse Events (CTCAE) version 4.03. The severity of cytokine release syndrome (CRS) will be assessed according to the grading described by Lee et al. (2014 and 2019,^{2,3} See [Appendix 5](#)). For the purpose of dose escalation, the DLT observation period will be up to the end of Cycle 1 in each patient. For those patients receiving a priming dose, Cycle 0 and Cycle 1 would be included in the DLT observation period. DLT evaluable patients will include patients that have experienced a DLT in the DLT observation period or. DLT evaluable patients will also include those who received all of their planned doses of PF-06863135 in the initial DLT observation period if Q2W dosing is being evaluated or at least all but one of their planned doses of PF-0686135 if Q1W dosing is being evaluated, provided a dose was not missed due to toxicity attributed to study drug. Safety information from any patients that do not meet DLT evaluable criteria could still be considered for overall dose escalation decisions although they would not factor into mTPI decision rules.

Any of the following adverse events observed within the DLT observation period considered related to PF-06863135 or PF-06863135 in combination with lenalidomide, pomalidomide, dexamethasone, will be classified as DLTs:

Hematological:

- Grade 4 neutropenia lasting >5 days. Except in lenalidomide combination cohort where it can be managed by dose reduction of lenalidomide in the next cycle.
- Febrile neutropenia (defined as an absolute neutrophil count [ANC] <1000/mm³ with a single temperature of >38.3°C [101°F], or a sustained temperature of ≥38°C [100.4°F] for more than one hour). If fever is determined to be a symptom of CRS confirmed by clinical course and cytokine levels and resolves in a manner consistent with CRS, this would no longer be considered a DLT, and the patient may resume treatment.
- Grade ≥3 neutropenia with infection.
- Grade 4 thrombocytopenia (unless the study entry baseline count was ≥25,000 and <50,000 to take into account bone marrow suppression due to multiple myeloma, in

PF-06863135

C1071001

Final Protocol Amendment 9, 28 March 2023

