5.5.1. Dosing Interruptions

Patients experiencing Grade 3 or 4 potentially treatment-related toxicity or intolerable drug-related Grade 2 toxicity despite supportive care should have their treatment interrupted.

Appropriate follow-up assessments should be done until adequate recovery occurs as assessed by the investigator. Criteria required before treatment can resume are described in the Dose Delays Section 5.5.2.

Doses may be held as needed until toxicity resolution. Depending on when the adverse event resolved, a treatment interruption may lead to the patient missing all subsequent planned doses within that same cycle or even to delay the initiation of the subsequent cycle.

If the adverse event that led to the treatment interruption recovers within the same cycle, then re-dosing in that cycle is allowed. Doses omitted for toxicity are not replaced within the same cycle. The need for a dose reduction at the time of treatment resumption should be based on the criteria defined in the Dose Reductions Section 5.5.3, unless expressly agreed otherwise following discussion between the investigator and the sponsor.

In the event of a treatment interruption for reasons other than treatment-related toxicity (eg, elective surgery) lasting >3 weeks, treatment resumption will be decided in consultation with the sponsor.

PF-06863135
C1071001
Final Protocol Amendment 9, 28 March 2023

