5.5.2. Dose Delays

Re-treatment following treatment interruption for treatment-related toxicity or at the start of any new cycle should not occur until all of the following parameters have been met:

- ANC $\geq 1,000/\text{mm}^3$ for PF-06863135, dexamethasone, and lenalidomide; $\geq 500/\text{mm}^3$ for pomalidomide;
- Platelets count $\geq 25,000/\text{mm}^3$ for PF-06863135 and dexamethasone; $\geq 30,000/\text{mm}^3$ for lenalidomide; $\geq 50,000/\text{mm}^3$ for pomalidomide;
- Non-hematologic toxicities have returned to baseline or Grade ≤ 1 severity (or, at the investigator's discretion, Grade ≤ 2 if not considered a safety risk for the patient).
- Recovery of treatment-emergent peripheral neuropathy to Grade ≤ 1 severity.

If a treatment delay results from worsening of hematologic or biochemical parameters, the frequency of relevant blood tests should be increased as clinically indicated.

If these conditions are met within 3 weeks of treatment interruption or cycle delay, study treatment may be resumed. Refer to the Dose Reductions Section 5.5.3 for adverse events requiring dose reduction at the time of treatment resumption.

If these conditions are not met, treatment resumption must be delayed up to a maximum of 3 weeks. If patients require discontinuation of study treatment for more than 42 days of Day 1 of the current cycle, then study treatment should be permanently discontinued, unless the investigator's benefit/risk assessment suggests otherwise after discussion with the Sponsor's medical monitor.

If a treatment interruption continues beyond the last day of the current cycle, then the day when treatment is restarted will be counted as Day 1 of the next cycle.

Recommended guidelines for dose delays of PF-06863135 for participants who have active [confirmed (positive by regulatory authority-approved test) or presumed (test pending/clinical suspicion)] SARS-CoV2 infection can be found in [Appendix 10](#).

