5.5.3. Dose Reductions

Following dosing interruption or cycle delay due to toxicity, the PF-06863135 dose may need to be reduced when treatment is resumed.

No specific dose adjustments for PF-06863135 are recommended for Grade 1/2 treatment-related toxicity. However, investigators should always manage their patients according to their medical judgment based on the particular clinical circumstances.

Patients experiencing recurrent and intolerable Grade 2 toxicity may resume dosing at the next lower dose level of PF-06863135 once recovery to Grade ≤ 1 or baseline is achieved.

PF-06863135

C1071001

Final Protocol Amendment 9, 28 March 2023

Dose reduction of PF-06863135 by 1 and, if needed, 2 dose levels will be allowed depending on the type and severity of toxicity encountered. Patients enrolled in the first (0.1 µg/kg) cohort will be allowed 1 dose reduction if required. Patients requiring more than 2 dose reductions (or 1 dose reduction for the first cohort) will be discontinued from the treatment and entered into the follow-up phase, unless otherwise agreed between the investigator and the sponsor. If dose reduction of PF-06863135 is needed for any patient who receives fixed doses of PF-06863135 (Parts 1C, 1D, 1E, 2A, 2C, 2D, 2E), the next dose level of PF-06863135 will be 25% lower than the current dose level (eg, from 32 mg to 24 mg, or from 24 mg to 16 mg). All dose modifications/adjustments must be clearly documented in the patient's source notes and case report form (CRF).

Once a dose has been reduced for a given patient, all subsequent cycles should be administered at that dose level, unless further dose reduction is required. Intrapatient dose re-escalation is not allowed.

Patients experiencing a DLT may resume dosing at the next lower dose level (if applicable) once adequate recovery is achieved. Patients experiencing a DLT of prolonged myelosuppression (>42 days) may not resume treatment even if adequate recovery is achieved. No dose reductions are planned for patients experiencing toxicities other than those listed as DLTs. However, patients experiencing recurrent and intolerable Grade 2 toxicity may resume dosing at the next lower dose level once recovery to Grade ≤1 or baseline is achieved. Patients whose hematologic indices improve prior to meeting the criteria for prolonged myelosuppression >42 days may resume dosing at the next lower dose level or permanently discontinue from treatment at the discretion of the investigator.

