Recommended dose reductions for PF-06863135 are described in Table 5.

Table 5. Dose Modifications for PF-06863135 Product-Related Toxicity and for Peripheral Sensory or Motor Neuropathy***

| Toxicity | Grade 1 | Grade 2 | Grade 3 | Grade 4 |
|--|----------------------------------|----------------------------------|--|--|
| Non-hematologic (excluding peripheral neuropathy-see below) | Continue at the same dose level. | Continue at the same dose level. | Withhold dose until toxicity is Grade ≤1, or has returned to baseline, then reduce the dose by 1 level.* | Permanently discontinue.* |
| Hematologic except for lymphopenia, which is expected as part of PF-06863135 mechanism of action | Continue at the same dose level. | Continue at the same dose level. | Withhold dose until toxicity is Grade ≤2, or has returned to baseline, then resume treatment at the same dose level.** If toxicity reoccurs, dosing may be reduced by 1 dose level. If | Withhold dose until toxicity is Grade ≤2, or has returned to baseline, then reduce the dose by 1 level and resume treatment.** If toxicity reoccurs despite dose reduction, dosing may be reduced by |

PF-06863135
C1071001
Final Protocol Amendment 9, 28 March 2023

Table 5. Dose Modifications for PF-06863135 Product-Related Toxicity and for Peripheral Sensory or Motor Neuropathy***

| Toxicity | Grade 1 | Grade 2 | Grade 3 | Grade 4 |
|--|--|---|--|--|
| | | | 
toxicity reoccurs after a maximum of 2 dose level reductions (1 for patients in first cohort), patient may be permanently discontinued from treatment.
 
For platelets, withhold dose if toxicity $\leq 25,000 \text{ mm}^3$ and re-start when platelets have returned to $\geq 25,000 \text{ mm}^3$ or baseline
 | 1 more dose level. If toxicity reoccurs, patient may be permanently discontinued from treatment. |
| Peripheral sensory or motor neuropathy (all causality) See Section 8.4.4 for recommended work-up. | 
Continue at the same dose level.
 
Continue to monitor the participant for signs of worsening neuropathy
 | 
Withhold dose until resolution to Grade ≤ 1, then resume at a reduced dose level.
 
Continue to monitor the participants for signs of worsening neuropathy.
 
If Grade ≥ 2 neuropathy reoccurs, permanently discontinue elranatamab.
 | Permanently discontinue elranatamab. | Permanently discontinue elranatamab |

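### Table 5 gives two platelet restart counts after a fall below 25,000/mm3, and at exactly 25,000 its platelet line both withholds and restarts PF-06863135

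*Protocol*

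**What the plan says.** All references are to the Protocol.

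- **Table 5, hematologic row, Grade 3 cell.** The general rule is to hold until Grade 2 or better, or baseline, and then resume at the same dose level. The cell ends with a separate line that begins "For platelets, withhold dose if toxicity". As extracted, it holds at 25,000/mm3 or below and restarts at 25,000 or above, or at baseline.
- **Table 5, hematologic row, Grade 4 cell.** "Withhold dose until toxicity is Grade ≤2, or has returned to baseline, then reduce the dose by 1 level and resume treatment". There is no exception for platelets and no pointer to the platelet line.
- **Section 5.5.1.** "Criteria required before treatment can resume are described in the Dose Delays Section 5.5.2".
- **Section 5.5.2.** Re-treatment must wait until every listed parameter is met. For PF-06863135 the platelet parameter is at least 25,000/mm3. Then: "If these conditions are met within 3 weeks of treatment interruption or cycle delay, study treatment may be resumed". Stopping treatment "for more than 42 days of Day 1 of the current cycle, then study treatment should be permanently discontinued", unless the investigator judges otherwise after discussion with the sponsor's medical monitor.
- **Section 3.2.** The DLT list includes "Grade 4 thrombocytopenia (unless the study entry baseline count was ≥25,000 and <50,000", with further conditions for that baseline band.

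**The concern.** A dosing rule should give one instruction for one platelet count. Here, an investigator who reads down the Grade 4 column and one who reads the platelet line can restart the same patient at different counts. No text says which rule yields. The stricter reading also lengthens the hold and moves the patient toward the 42-day provision. The looser reading re-exposes the patient at a lower count. At 25,000 itself, the line cannot be followed as printed.

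**Working it through.** The plan states no figure to reproduce, so the check sets the rules side by side.

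**Inputs.** Let x be the current count (per mm3), b the patient's baseline, and L the lowest count that is Grade 2.

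| Rule | Hold | Restart |
|---|---|---|
| Platelet line (Grade 3 cell) | x ≤ 25,000 | x ≥ 25,000, or baseline |
| Grade 4 cell | Grade 4 | x ≥ min(L, b) |
| Section 5.5.2 | – | not before x ≥ 25,000 |

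**Step 1: which counts are Grade 4.** The protocol grades by CTCAE 4.03 but does not print the platelet limits. Section 3.2 treats a baseline of 25,000 to below 50,000 as the band next to Grade 4. Counts below 25,000 are therefore read as Grade 4, and L is taken as about 50,000. Both are inferences.

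**Step 2: the platelet line has to reach Grade 4 counts.** If Grade 3 starts at 25,000, a hold at x ≤ 25,000 confined to Grade 3 would act at one value only. The line is useful only if it also covers counts below 25,000, and the Grade 4 cell covers those too.

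**Step 3: where the two cells differ.** The line allows restart and the Grade 4 cell does not when 25,000 ≤ x < min(L, b). The width of that range is min(L, b) − 25,000.

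- L = 50,000, b = 25,000: width 0.
- L = 50,000, b = 30,000: 30,000 − 25,000 = 5,000.
- L = 50,000, b = 40,000: 40,000 − 25,000 = 15,000.
- L = 50,000, b of 50,000 or more: 50,000 − 25,000 = 25,000.
- Range for the assumption: the largest width is 15,000 if L = 40,000 and 50,000 if L = 75,000.

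**Step 4: one patient.** Take b = 60,000, a lowest count of 15,000, and recovery to 30,000. The line allows restart, since 30,000 ≥ 25,000. The Grade 4 cell needs min(50,000, 60,000) = 50,000, so it keeps holding. With L = 40,000 it needs 40,000; with L = 75,000 it needs min(75,000, 60,000) = 60,000. The conflict for this patient does not depend on the choice of L within that range.

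**Step 5: the boundary.** At x = 25,000, both x ≤ 25,000 and x ≥ 25,000 are true. Other platelet rules in the same section avoid this. Table 6 holds lenalidomide below 30,000 and resumes at 30,000 or above. Table 9 holds pomalidomide below 25,000 and resumes around 50,000.

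**The case against.** The best reply is that the specific rule governs the general one. The line is expressly about platelets, and it matches both the 25,000 in Section 5.5.2 and the 25,000 entry count for monotherapy in Section 4.1. The Grade 4 cell would then supply only the dose. This is plausible and may be what the sponsor meant. But no text says so, and the line is printed in a different grade column from most of the patients it would govern.

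Four stronger readings are tempting, and the documents do not support them.

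- **That Section 5.5.2 contradicts the Grade 4 cell.** Section 5.5.1 does send the reader there. But 5.5.2 sets a minimum and then permits resumption; a stricter cell is compatible with a minimum.
- **That each study part has its own fixed gap.** The size depends on the unprinted Grade 2 limit. Lenalidomide and pomalidomide also have their own restart counts in 5.5.2 (30,000 and 50,000), which limit the practical effect in the combination parts.
- **That many patients are affected.** Section 1.2.3.1 reports thrombocytopenia in 48.8% of 41 patients at the full dose, that is 20 of 41. This is any grade. The number who fell below 25,000 is not given.
- **That the restart dose is also undefined.** The Grade 4 cell says one level lower, and 5.5.3 agrees: "Patients whose hematologic indices improve prior to meeting the criteria for prolonged myelosuppression >42 days may resume dosing at the next lower dose level". The sentence "No dose reductions are planned for patients experiencing toxicities other than those listed as DLTs" sits awkwardly beside this, but it does not change the restart count.

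It is also fair to say that both parts rest on text extracted from a table that breaks across a page. If the platelet line spans both grade columns in the source, part 1 falls. If the hold sign is strictly below 25,000, part 2 falls.

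**Conclusion.** As extracted, Table 5 contradicts itself in two places. First, for a patient recovering from below 25,000 with a baseline above the current count, the platelet line and the Grade 4 cell differ from 25,000 up to the Grade 2 limit. That is up to 25,000/mm3 wide if the limit is 50,000. Second, a count of exactly 25,000 is both held and restarted.

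This is a minor wording error in a safety rule. Table 5 is introduced as recommended, 5.5.3 leaves recovery to the investigator's assessment, and the 42-day stop can be overridden. Enrollment is complete, with 101 patients at the June 2022 cutoff. No endpoint, DLT criterion or estimate uses the line. The conclusion assumes that Grade 4 means below 25,000 and that the column position and sign are as extracted.

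**What to change.** Check the source PDF for the column position and the sign. If they are as extracted:

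1. Change the hold trigger in the platelet line to below 25,000/mm3.
2. Print one platelet restart count that applies in both the Grade 3 and Grade 4 cells, so that a deeper fall never has a laxer restart than a shallower one. There are two ways:
   - Add a pointer in the Grade 4 cell to the platelet line (restart at 25,000 or above, or baseline, one dose level lower), and state that the line also governs Grade 3 platelets.
   - Delete the 25,000 restart from the line and keep Grade 2 or better, or baseline, in both cells.

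The sponsor's medical team should choose the count. Section 5.5.2 can stay as a minimum under either choice. The 25,000 restart should not be limited to patients recovering from below 25,000. On the assumed grades, a patient who fell to 15,000 could then restart at 25,000, while one who fell only to 30,000 would wait for about 50,000 or baseline.

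The cost is a few words in Table 5, with no new data, patients or analyses.

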5.5.4. Intra-Patient Dose Escalation for PF-06863135

Once a patient completes their 60 day late toxicity observation period, if the patient did not experience any ≥ Grade 3 drug related toxicities, the patient may escalate to the next higher dose level if the higher dose level is already been declared safe following 60-day late toxicity evaluation, and criteria outlined in [Section 3.1.4.1 Criteria for Intrapatient Dose Escalation](#) have been met.

Additional intra-patient dose escalations will also be permitted once additional 60 day late toxicity evaluation has been completed, and if the patient did not experience any ≥ Grade 3 drug related toxicities. No crossover is allowed, however, between monotherapy PF-06863135 and the different combination regimens.

A maintenance dose level will be declared safe following DLT evaluation of patients for a minimum of 60 days. Once a maintenance dose level has been declared safe, patients at lower dose levels who have completed the 60 day late toxicity observation period may escalate to the next higher dose level, if criteria outlined in [Section 3.1.4.1 Criteria for Intrapatient Dose Escalation](#) have been met. No crossover is allowed, however, between monotherapy PF-06863135 and the different combination regimens.

PF-06863135
C1071001
Final Protocol Amendment 9, 28 March 2023

5.6. Permanent Discontinuation

The study will stop if all doses explored appear to be overly toxic as determined by study sponsor and investigators. For other sponsor discontinuation criteria, please refer to [Section 14](#). For patient withdrawal criteria, please refer to [Section 6.6](#).

Note that disease progression as determined by laboratory assessments completed within the first cycle cannot be a reason for study withdrawal.

Dose escalation may also stop if:

- The maximum sample size has been achieved;
- Approximately 6-16 patients have been enrolled at a dose that is predicted to be the MTD/MAD;
- All doses explored appear to be overly toxic and the MTD/MAD cannot be determined.

5.7. Investigational Product Storage

The investigator, or an approved representative, eg, pharmacist will ensure that all investigational products are stored in a secured area with controlled access under required storage conditions and in accordance with applicable regulatory requirements.

Investigational products should be stored in their original containers and in accordance with the labels.

See the IP manual for storage conditions of the product once reconstituted.

Any storage conditions stated in the SRSD will be superseded by the storage conditions stated on the product label.

Site systems must be capable of measuring and documenting (for example, via a log), at a minimum, daily minimum and maximum temperatures for all site storage locations (as applicable, including frozen, refrigerated, and/or room-temperature products). This should be captured from the time of investigational product receipt throughout the study. Even for continuous-monitoring systems, a log or site procedure that ensures active evaluation for excursions should be available. The intent is to ensure that the minimum and maximum temperature is checked each business day to confirm that no excursion occurred since the last evaluation and to provide the site with the capability to store or view the minimum/maximum temperature for all nonworking days upon return to normal operations. The operation of the temperature monitoring device and storage unit (for example, refrigerator), as applicable, should be regularly inspected to ensure they are maintained in working order.

Any excursions from the product label storage conditions should be reported to Pfizer upon discovery. The site should actively pursue options for returning the product to the storage

PF-06863135

C1071001

Final Protocol Amendment 9, 28 March 2023

conditions described in the labeling, as soon as possible. Deviations from the storage requirements, including any actions taken, must be documented and reported to Pfizer.

Once an excursion is identified, the investigational product must be quarantined and not used until the Pfizer provides permission to use the investigational product. It will not be considered a protocol deviation if Pfizer approves the use of the investigational product after the temperature excursion. Use of the investigational product prior to Pfizer approval will be considered a protocol deviation.

Specific details regarding information the site should report for each excursion will be provided to the site.

Receipt of materials, door opening and closing, and other routine handling operations where the products are briefly out of the temperature range described in the labeling are not considered excursions.

5.8. Investigational and Non-Investigational Product Accountability

The investigator site must maintain adequate records documenting the receipt, use, loss, or other disposition of the investigational and non-investigational product supplies. All investigational and non-investigational products will be accounted for using a drug accountability form/record.

5.8.1. Destruction of Investigational and Non-Investigational Product Supplies

The sponsor or designee will provide guidance on the destruction of unused investigational and non-investigational product (eg, at the site). If destruction is authorized to take place at the investigator site, the investigator must ensure that the materials are destroyed in compliance with applicable environmental regulations, institutional policy, and any special instructions provided by Pfizer, and all destruction must be adequately documented.

